## 10. SAFETY AND REPORTING REQUIREMENTS

This study will be conducted in accordance with Health Canada regulatory requirements and ICH Good Clinical Practice Guidelines. Adverse Events (AEs) and Serious Adverse Events (SAEs) data will be reported and collected.

### 10.1 Adverse Event Definitions

An **adverse event** (AE) is any untoward medical occurrence in a clinical investigation patient who is administered a drug or biologic (medicinal product) during the course of a study, which does not necessarily have to have a causal relationship with this treatment. An AE can therefore be any unfavorable and unintended sign (including an abnormal laboratory finding), symptom, or disease temporally associated with the use of an investigational product, whether or not considered related to the investigational product. Each AE is to be classified by the investigator as serious or non-serious.

Disease signs, symptoms, and/or laboratory abnormalities already existing prior to the use of the product are not considered AEs after administration of the study product unless they reoccur after the patient has recovered from the pre-existing condition or they represent an exacerbation in intensity or frequency.

A laboratory test abnormality considered clinically relevant (e.g. causing the patient to withdraw from the study, requiring treatment or causing apparent clinical manifestations) or judged relevant by the Investigator should be reported as an AE.

### 10.2 Adverse Event Documentation

Adverse events will use the descriptions and grading scales found in the revised NCI CTCAE. This study will utilize the CTCAE Version 5.0 for AE reporting.

All AEs must be recorded in the eCRFs. Documentation must be supported by an entry in the patient's file. Each event should be described in detail along with start and stop dates, severity, relationship to investigational product as judged by the QI, action taken and outcome.

### 10.3 Attribution Definitions

For all AEs, relationship to **each of the** study drugs will be reported on the appropriate AE eCRF page. The PI must judge whether **each of the** study drugs caused or contributed to the AE in which case it is considered to be an adverse drug reaction (ADR), and report it as either:

**Related (definitely, probably or possibly):** there is a reasonable possibility that the investigational product caused or contributed to the AE; this conclusion may be supported by the following observations, though these are not required for the determination of relatedness:

- There is a plausible time sequence between onset of the AE and investigational product administration;
- There is a plausible biological mechanism through which the investigational product may have caused or contributed to the AE.

**Not related (unrelated, unlikely related):** It is highly unlikely or impossible that the investigational product caused or contributed to the AE; this conclusion may be supported by the following observations, though these are not required for a determination of not related:

- Another cause of the AE is evident and most plausible; the temporal sequence is inconsistent between the onset of the AE and investigational product administration; a causal relationship is considered biologically implausible.

#### **10.4 Serious Adverse Event**

A **Serious Adverse Event (SAE) or Reaction** is any untoward medical occurrence that at any dose:

- Results in death
- Is life-threatening
- Requires in-patient hospitalization or prolongation of existing hospitalization
- Results in persistent or significant disability/incapacity
- Is a congenital anomaly / birth defect
- Is an important medical event that may not be immediately life threatening or result in death or hospitalization, but may jeopardize the patient and may require medical or surgical intervention to prevent one of the outcomes listed above (example: intensive treatment in an emergency room or at home for bronchospasm, convulsions that do not result in hospitalization). Medical and scientific judgment should be exercised in deciding whether some events should be considered as serious because their quick reporting to the sponsor may be of interest for the overall conduct of the study.

**Life-threatening:** The term “life-threatening” in the definition of “serious” refers to an adverse event in which the patient was at risk of death at the time of the event. It does not refer to an adverse event that hypothetically might have caused death if it were more severe.

**Hospitalization:** Any AE leading to hospitalization or prolongation of hospitalization will be considered as Serious, UNLESS at least one of the following exceptions are met:

- The admission results in a hospital stay of less than 12 hours.
- OR**
- The admission is pre-planned (i.e., elective or scheduled surgery arranged prior to day 1 of the study or for prophylactic insertion of a gastric feeding tube).

---

---

**OR**

- The admission is not associated with an adverse event (e.g. social hospitalization for purposes of respite care).

However, it should be noted that invasive treatment during any hospitalization may fulfil the criteria of ‘medically important’ and as such may be reportable as a serious adverse event dependent on clinical judgement. In addition where local regulatory authorities specifically require a more stringent definition, the local regulation takes precedent.

**Disability** means a substantial disruption of a person’s ability to conduct normal life’s functions.

**Important medical event:** Any AE may be considered serious because it may jeopardize the patient and may require intervention to prevent another serious condition.

Any death (regardless of cause) that occurs from the time of administration of the first dose of study therapy until 28 days after the final administration of the investigational product, and any death occurring after this time that is judged at least possibly related to prior treatment with the investigational product, will be promptly reported.

An AE is **unexpected** when the nature or severity of the AE is not consistent with the applicable product information (i.e. investigator’s brochure for an unapproved investigational product or package insert/summary of product characteristics for an approved product). An AE is considered to be associated with the use of the drug if the attribution is classified as “possible”, “probable” or “very likely”.

### **10.5 Adverse Events of Special Interest**

An adverse event of special interest (AESI) is an AE (serious or non-serious) of scientific and medical concern specific to the Sponsor’s product or program, for which ongoing monitoring and rapid communication by the Investigator to the Sponsor is required. Such events may require further investigation in order to characterize and understand them. AESIs may be added, modified, or removed during a study by protocol amendment.

AESIs for this study include:

- Grade  $\geq 3$  infections: Severe infections (e.g., bacterial, viral, or fungal) that are life-threatening or require significant medical intervention.
- Secondary malignancies: New cancers that develop during the study, potentially linked to the treatment.
- Grade  $\geq 3$  blood pressure changes: Severe hypertension or hypotension that could pose significant health risks.
- Grade  $\geq 3$  ALT, AST, and bilirubin: Severe liver function abnormalities, indicated by elevated levels of alanine aminotransferase (ALT), aspartate aminotransferase (AST), or bilirubin, suggesting potential liver toxicity.

- Symptomatic overdoses: Any symptoms resulting from taking higher-than-prescribed doses of ruxolitinib or belumosudil, requiring immediate attention.

These AESIs are monitored closely to ensure participant safety and to gather data on the safety profile of the combination therapy for cGvHD.

### **10.6 Adverse Event Reporting Criteria**

AEs are to be recorded within the CRF. Whenever possible, symptoms should be grouped as a single syndrome or diagnosis. The investigator should specify the date of onset, grade, action taken with respect to the investigational product, corrective treatment or therapy given, outcome and his/her opinion as to whether there is a reasonable possibility that the AE was related to the investigational product.

The severity of all AEs will be graded according to the NCI CTCAE, version 5.0. For each event, the highest severity grade attained since the last assessment period will be reported.

### **10.7 Adverse Event Reporting Period and Follow up of AEs, SAEs, and AESIs**

The AE reporting period begins at the time the patient receives their first dose of study treatment (i.e., C1D1). All AEs, SAEs and AESIs must be followed until resolution or 28 days following the last dose of study treatment, whichever comes first. The QI shall provide follow-up information when available in a new follow-up SAE form. Resolution status of such an event should be documented on the eCRF.

Patients withdrawn from the study due to an AE will be followed until the AE has resolved. In the case of an SAE, the patient will be followed until clinical recovery or until progression has been stabilized or judged to be chronic. After discontinuation from protocol treatment, all patients will be followed for any ongoing or late toxicities. Patients will be seen for a Safety Follow up visit,  $28 \pm 7$  days after discontinuing treatment. Safety Follow up procedures will be completed as indicated in the Study Calendar.

The AE reporting period will end once 28 days have passed since the patient's last dose of study drug. Therefore, SAEs occurring after the last dose of study treatment that have been deemed by the QI as at least possibly related to protocol treatment, must be reported if it occurs within 28 days after discontinuation of the investigational products. In addition, any known untoward event of any severity that occurs subsequent to the AE reporting period that the Investigator assesses as at least possibly related to the study therapy (i.e., the relationship cannot be ruled out) should also be reported as an AE. Ongoing and non-resolved toxicities are followed until resolution back to baseline or  $\leq$  Grade 1 after off treatment, or until considered stable by the QI.

---

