## 10.8 Serious Adverse Event Reporting to Ozmosis

All SAEs defined as per Section 10.4 and all AESIs defined as per Section 10.5 must be recorded on case report forms. In addition, they must be reported to Ozmosis according to the following instructions:

1. Within 24 hours of becoming aware of the event, report initial information (on trial specific SAE report form) by fax or e-mail to:

Ozmosis Research Inc.  
[contact]  
E-mail: [[contact]](mailto:[contact])

- The initial information should always contain:
    - Name of reporter/Site Investigator,
    - Patient identification,
    - AE Term,
    - Investigational product dose and start/stop dates
2. On the next working day *if the initial report in step #1 did not contain complete information*: Fax or email completed trial-specific SAE form.
  3. Follow-up SAE and AESI reports should be submitted to Ozmosis as soon as possible.

All SAEs must be followed until resolved, become chronic, or stable unless the patient is lost to follow up. Resolution status of such an event should be documented on the eCRF.

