### **Responsibility for Reporting SAEs (including Pregnancies as applicable) and AESIs to Sponsor**

Ozmosis Research Inc. will be responsible for submitting all SAEs and AESIs (initial and/or follow-up reports) to the Sponsor using the SAE Report Form and pregnancies using the Pregnancy Report Form. The form must be emailed to Sponsor at the latest within 24 hours after Ozmosis receives it from the site. The foregoing is applicable to all SAEs, irrespective of causality.

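### Section 10.7 ties SAE reporting in the 28 days after the last dose to investigator-judged relatedness, contrary to Sections 10.8 and 10.2, so sites may capture these events inconsistently

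*Protocol*

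**What the plan says.** Protocol Section 10.7 fixes the reporting period at both ends. At the start, "The AE reporting period begins at the time the patient receives their first dose of study treatment". At the other end, "The AE reporting period will end once 28 days have passed" since the last dose. Neither statement mentions causality. The next sentence, presented as a consequence, covers SAEs after the last dose that are "deemed by the QI as at least possibly related to protocol treatment, must be reported if it occurs within 28 days after discontinuation of the" study drugs. The sentence after that asks for events later than the reporting period to be reported if the investigator cannot rule out a relation to study therapy.

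Other sections set the scope differently:

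- Section 10.8, on what sites send to the CRO: "All SAEs defined as per Section 10.4 and all AESIs defined as per Section 10.5 must be recorded on case report forms". Sites must also report them to the CRO within 24 hours of becoming aware. No causality condition is given.
- Section 10.2 asks for every AE to be entered in the eCRF. Section 10.1 defines an AE whether or not it is thought to be related.
- Section 10.10, on what the CRO sends to the sponsor: "The foregoing is applicable to all SAEs, irrespective of causality".
- Section 10.4, on deaths: "Any death (regardless of cause) that occurs from the time of administration of the first dose of study therapy until 28 days after the final" dose is to be reported promptly.

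Sections 3 and 11.3.1 define the primary safety endpoint as AEs over the duration of treatment. Section 11.3.1 summarises AEs, SAEs and AESIs by, among other things, relationship to study drug.

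**The concern.** A reporting period without a causality limit does not lead to an SAE rule with one. Read restrictively, Section 10.7 sets a narrower duty for serious events than for non-serious ones in the same 28 days, because non-serious AEs carry no relatedness test. It also applies the same test inside the window as after it, so for many non-fatal SAEs the end of the window would change nothing.

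What is at stake is complete and uniform capture of SAEs just after treatment stops. The trial is single-arm and open-label, so there is no control group against which to read post-treatment events, and each attribution is made by someone who knows the treatment. If the decision to report depends on that attribution, nobody downstream can review it for the events that were not sent. Any loss would also run one way, toward fewer SAEs.

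**Working it through.** No figure in the protocol is in dispute. The check sets the reporting rules side by side and follows one event through them.

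**Rules for an SAE between day 1 and day 28 after the last dose**

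- Section 10.7, reporting period: inside the period, no causality test.
- Section 10.7, following sentence: reportable if judged possibly related or more.
- Section 10.8: recorded and reported by the site, no causality test.
- Section 10.2: in the eCRF, no causality test.
- Section 10.4: if fatal, reported whatever the cause.
- Sections 10.5 and 10.8: if also an AESI (for example a Grade 3 or higher infection, liver-test abnormality or blood-pressure change), reported with no causality test.
- Section 10.9: progressive disease and relapse of the primary malignancy are not reportable as SAEs.

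**Worked case.** Ten days after the last dose a patient is admitted for several days with bleeding and a low platelet count. The investigator judges this unrelated to either drug. The admission makes it serious under Section 10.4. It is not fatal, not on the Section 10.5 list, and neither progression nor relapse. Section 10.8 requires a report within 24 hours. A site that takes the Section 10.7 sentence as its post-treatment rule would send none. Two sites could each point to a protocol sentence and act differently.

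**What is left after the other rules.** The conflict matters for SAEs that are all of the following: after the last dose, within 28 days, non-fatal, not AESIs, not exempt under Section 10.9, and judged unrelated.

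**Which passages conflict.** At site level the conflict is with Section 10.8, with Section 10.2, and with Section 10.7's own period. The all-causality sentence in Section 10.10 governs what the CRO forwards once a site has reported, so it is only indirect support. Expedited reporting to Health Canada in Section 10.10 is limited to serious, unexpected and related events; that is a separate duty and does not conflict.

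**Size of the window.** Share of the reporting period that falls after treatment = 28 / (days on treatment + 28).

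- 52 weeks of treatment, 364 days: 28 / 392 = 7.1%.
- 52 weeks plus the 4-week belumosudil taper of Section 5.4, 392 days: 28 / 420 = 6.7%.
- Stopping at 8 weeks, 56 days (an assumed example): 28 / 84 = 33%.

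These are shares of time, not of events. The number of SAEs affected would be patients entering the window × the proportion with such an SAE × the proportion judged unrelated. The protocol gives neither proportion, so no count follows.

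**The case against.** The strongest defence is that Section 10.7 never says only. It says that related SAEs must be reported; it does not exempt unrelated ones. The sentence before it, together with Sections 10.2 and 10.8, already requires everything to be recorded, and the study calendar shows AE collection as continuous. On this view the sentence is redundant and harmless. Part of that stands: under-reporting is a risk that depends on how a site reads one sentence, not a certain result. The conflict remains, however, because the condition has no purpose unless it restricts, and it sits in the section that defines the reporting period.

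It is also fair that most of the gravest events are protected. Deaths are covered by Section 10.4 and AESIs by Sections 10.5 and 10.8. Some flares of cGvHD may fall under the Section 10.9 exemption in any case. This narrows the point to the class of events described in the check.

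A reader might infer three stronger things that the protocol does not support:

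- **That the primary safety endpoint loses SAEs.** The endpoint is defined over the duration of treatment, so events after the last dose are not clearly part of it. What can be said is that the endpoint window and the reporting window are not aligned.
- **That events are withheld from the DSMB.** Section 5.8 says that the DSMB reviews safety data twice a year under a charter that is not available here. Nothing limits its review to SAEs reported under the Section 10.7 sentence.
- **That a number of missing patients can be stated.** Any such figure would rest wholly on assumed rates.

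**Conclusion.** The contradiction is real and rests on the text alone. Section 10.7 makes SAE reporting in the 28 days after the last dose depend on the investigator's attribution, while Section 10.8 and Section 10.2 impose no such condition. The consequence is possible inconsistent capture, across sites, of non-fatal SAEs that are not AESIs and are judged unrelated. The window is about 7% of the reporting period for a patient who completes 52 weeks and more for one who stops early; these shares assume that the last dose falls at week 52, at the end of the taper, or at the assumed early stop. The number of events cannot be derived from the protocol. This is a modest defect in a reporting rule. It is still worth correcting before enrolment is far advanced, because events not collected at the time are hard to recover later.

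**What to change.** Reword Section 10.7 so that all AEs, SAEs and AESIs, regardless of causality and subject to the exceptions in Section 10.9, are reported from the first dose until 28 days after the last dose. Keep the relatedness condition only for events after that period, as the section's following sentence already does. Then add a statement in Section 11.3.1, consistent with Section 3, on whether events in the 28-day window count in the primary safety summary or are tabulated separately. Rewording Section 10.7 alone would not settle that.

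The cost is one or two sentences, a few more SAE forms, and possibly a slightly higher reported SAE incidence. Neither treatment nor the visit schedule changes.

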## 10.8 Serious Adverse Event Reporting to Ozmosis

All SAEs defined as per Section 10.4 and all AESIs defined as per Section 10.5 must be recorded on case report forms. In addition, they must be reported to Ozmosis according to the following instructions:

1. Within 24 hours of becoming aware of the event, report initial information (on trial specific SAE report form) by fax or e-mail to:

Ozmosis Research Inc.  
[contact]  
E-mail: [[contact]](mailto:[contact])

- The initial information should always contain:
    - Name of reporter/Site Investigator,
    - Patient identification,
    - AE Term,
    - Investigational product dose and start/stop dates
2. On the next working day *if the initial report in step #1 did not contain complete information*: Fax or email completed trial-specific SAE form.
  3. Follow-up SAE and AESI reports should be submitted to Ozmosis as soon as possible.

All SAEs must be followed until resolved, become chronic, or stable unless the patient is lost to follow up. Resolution status of such an event should be documented on the eCRF.

## 10.9 Exceptions and Non-Reportable SAEs

**Progressive disease**, death due to progressive disease, and relapse of primary malignancy, will not be reportable as an SAE in this study. Relapse of the underlying malignancy is not reported as an adverse event if it is clearly consistent with the suspected relapse. Clinical symptoms of relapse may be reported as an AE if the symptom cannot be determined as exclusively due to the relapse of the underlying malignancy or does not fit the expected pattern of relapse for the disease under study. If there is any uncertainty of an AE being due only to cancer it should be reported as an AE or SAE.

**Elective procedures** requiring hospitalization will not be considered SAE's if they were pre-planned prior to signing consent; however, other events may occur during this hospitalization that may be considered serious or non-serious adverse events and will need to be captured according to the protocol SAE reporting period if hospitalization is prolonged.

---

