**Doses held due to toxicity or missed will not be made up at a later time.**

### 5.3 Dose Modifications

#### **Ruxolitinib**

Dose reductions or interruptions for worsening cytopenias attributed to ruxolitinib are permitted in order to allow the patient to continue on the study treatment and should follow standard of care. For any patient who develops severe or worsening cytopenias necessitating abrupt interruption of ruxolitinib, a flare of cGvHD is expected to occur. To avoid a significant cGvHD flare during abrupt ruxolitinib interruption, the patient's corticosteroid dose should be maintained or increased to > 0.4 mg/kg/day methylprednisolone (or equivalent prednisone to > 0.5 mg/kg/day) for a minimum 7 days after abrupt cessation of ruxolitinib. Ruxolitinib dosing may be restarted or increased following recovery of the hematologic parameter(s) to what are considered acceptable levels per standard of care. The objective for restarting or escalating after a reduction for hematologic safety is to find the highest safe dosing regimen of ruxolitinib for each patient that is necessary to obtain a clinical response, with increases in dose not more than in increments of 5 mg BID and not more often than every 2 weeks.

If the reduced dose is tolerated for 4 weeks, the dose may be re-escalated to the previous dose.

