## **5.9 Safety Stopping Rules**

Accrual will be on hold and a meeting held with the PI, investigators and Data Safety Monitoring Board (DSMB) if the following occurs:

1. If there is a death or unacceptable toxicity (SAE Grade  $\geq 4$ ) attributed as: possibly, probably or definitely related to the study drug.
2. If the first 3 patients enrolled experience significant toxicity (i.e. Grade  $\geq 3$  AEs lasting 4 weeks or longer) attributed as: possibly, probably or definitely related to the study drug.

A decision will be made by the Sponsor and DSMB regarding whether the study will be re-opened for the next patient in the study or not. If there is disagreement in the SAE causality assessment or whether or not to re-open accrual between the different parties, the final decision will rest on the DSMB. Ozmosis will notify all sites and applicable parties on the decision and whether accrual has re-opened. Only when it is deemed safe can the next patient start the treatment phase of the study.

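### Sections 10.4 and 10.9 conflict on whether a death from progressive disease is a reportable SAE, and the undefined term may keep serious cGvHD worsening out of expedited review

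*Protocol*

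**What the plan says.** Section 10.4 lists "Results in death" among the seriousness criteria, with no exception by cause. It then sets a rule for deaths: "Any death (regardless of cause) that occurs from the time of administration of the first dose of study therapy until 28 days after" the final dose of investigational product "will be promptly reported". Later deaths are covered if judged at least possibly related to treatment.

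Section 10.8 gives the route: "All SAEs defined as per Section 10.4 and all AESIs defined as per Section 10.5 must be recorded on case report forms". They also go to the CRO within 24 hours of the site becoming aware. Section 10.10 has the CRO forward all SAEs to the sponsor within a further 24 hours, irrespective of causality.

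Section 10.9 exempts progressive disease and adds that "death due to progressive disease, and relapse of primary malignancy, will not be reportable as an SAE in this study". It does not mention the death rule in Section 10.4 and does not define progressive disease. The rest of the paragraph concerns relapse of the malignancy. Its closing safeguard, that doubtful events should be reported, applies only where it is uncertain that cancer alone is the cause.

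Two other sections bear on the point. Section 5.3 says that when ruxolitinib has to be stopped abruptly for cytopenia, "a flare of cGvHD is expected to occur". Section 5.9, stopping rule 1, puts accrual on hold "If there is a death or unacceptable toxicity" (the latter specified as an SAE of Grade 4 or higher) is at least possibly related to study drug. The DSMB has the final say where parties disagree on SAE causality.

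**The concern.** Safety and tolerability form a primary endpoint. The protocol also says that no prospective study has examined a combination of two non-first-line agents in cGvHD. Rules for reporting deaths and life-threatening events should therefore lead every site to the same action. Here two sites can each follow the protocol and treat the same death in opposite ways.

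The exemption resembles one written for a cancer trial, where progression of the tumour is the efficacy outcome. In this trial the treated disease is cGvHD. Worsening of cGvHD may be treatment failure, a consequence of drug toxicity that forced an interruption, or both. At stake are the completeness of SAE reporting and SAE tables, and whether someone other than the treating site looks promptly at causality when cGvHD and drug effects are hard to separate.

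**Working it through.** No arithmetic applies. The check sets the sections side by side and follows three cases through them.

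**What progressive disease means.** Section 10.9 lists relapse of primary malignancy as a separate item, so progressive disease should mean something else. Section 5.6 uses progression for cGvHD by NIH criteria. cGvHD is thus the natural reading, though not a stated one.

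**Case A: a death on treatment that the site ascribes to progression.**

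| Section | Consequence |
|---|---|
| 10.4 | An SAE, because it is a death; reported promptly whatever the cause |
| 10.8 | To the CRO within 24 hours |
| 10.10 | On to the sponsor, irrespective of causality |
| 10.9 | Not reportable as an SAE |

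The first three rows conflict with the last. This holds whether progressive disease means cGvHD or malignancy, because Section 10.4 makes no distinction by cause.

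**Case B: a non-fatal, life-threatening cGvHD flare after abrupt ruxolitinib interruption.** Section 10.1 counts a pre-existing condition that worsens in intensity or frequency as an AE. Being life-threatening, the flare is an SAE under Section 10.4. If the site classes it as progressive disease, Section 10.9 removes it from SAE reporting. It may then miss the limb of stopping rule 1 that is defined by SAE grade, and the DSMB's role in SAE causality. The safeguard for doubtful cases does not help, because the doubt is between cGvHD and drug, not cancer and drug.

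**Case C: a death judged at least possibly related to study drug.** In Section 5.9 the SAE qualifier attaches to unacceptable toxicity, not to death. By its wording, rule 1 is triggered whatever the SAE status. What Section 10.9 can remove is the expedited SAE report through which others would review the attribution.

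**What remains in all cases.**
- Section 10.3 requires attribution to each study drug for all AEs.
- The exemption from AE recording in Section 10.9 concerns relapse of the malignancy only, so cGvHD worsening that meets the AE definition is still recorded and graded.
- AESIs, including Grade 3 or higher infections and liver test abnormalities, go to the CRO within 24 hours (Sections 10.5 and 10.8).
- Survival status is collected at follow-up. FFS counts non-relapse mortality and progression or loss of response that requires a switch of systemic treatment (Section 11.3.1).
- The DSMB reviews safety data twice a year and may meet in between (Section 5.8).

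**The case against.** The best defence is that Section 10.9 is headed as exceptions and so qualifies Section 10.4. On that view, Section 10.4 asks only for prompt reporting and does not name the SAE form, while Section 10.9 says only that the event is not reportable as an SAE. This would work if the protocol gave another prompt route for deaths, but it gives none. The nearest is the 24-hour notice to the CRO when a patient discontinues (Section 5.6). Death is not on that section's list of reasons, and the section does not ask for seriousness or causality in the notice.

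It is also fair that the cGvHD reading is inferred. The rest of the Section 10.9 paragraph treats the malignancy as the disease under study. If malignancy was meant throughout, the argument about flares falls away, but the conflict over deaths stays. Nor does the protocol say that a flare after interruption must be classed as progression, and Section 5.3 sets out steps to avoid a significant flare. The weakness is that nothing prevents such classification.

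Exempting disease progression from SAE reporting can be a legitimate design choice. The objection here is to an undefined exemption that conflicts with another section.

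Three stronger readings are tempting and not supported. A reader might infer that cGvHD deaths cannot trigger the accrual hold; Case C shows that they can. A reader might infer that only SAE forms carry drug attribution; Section 10.3 requires it for every AE. A reader might also attach a number of unreported events; the protocol gives no rate of death or life-threatening worsening from cGvHD, so any count would rest on an invented rate.

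**Conclusion.** The point holds as a contradiction between Sections 10.4 and 10.8 on one side and Section 10.9 on the other, made worse by an undefined term and a safeguard that covers only cancer. The conflict over deaths rests on no assumption.

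The wider consequence is conditional. It assumes that progressive disease means cGvHD and that a site classes the event as progression. Under those conditions, fatal and Grade 4 or worse events may miss expedited SAE reporting and SAE tables, and the non-fatal ones may miss the SAE limb of stopping rule 1 and the DSMB's causality review. The effect is delayed or uneven review, not loss of the events from the trial's data.

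The exemption reaches all of up to 63 patients, over about 52 weeks of treatment and the 28 days after the last dose. The number of events affected cannot be derived from the document.

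**What to change.** Reconcile Sections 10.4, 10.8, 10.9 and 5.9 in one amendment:

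1. Define progressive disease in Section 10.9 as cGvHD, malignancy or both.
2. State that every death in the Section 10.4 window goes on the SAE form within 24 hours, whatever its cause, and that Section 10.9 does not override this.
3. Replace the cancer-only safeguard: a serious event is reported as an SAE whenever it is uncertain that it is due only to cGvHD or malignancy, including when it follows interruption or reduction of a study drug.
4. Make the wording of stopping rule 1 consistent with these definitions, so that it is clear which events classed as progression come to the DSMB.

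Making every serious cGvHD worsening an SAE, with a flag for preceding dose interruption, would go further. That is a debatable design choice and is not needed to remove the contradiction.

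The cost is about a paragraph of text and some extra SAE forms for events that prove to be disease-related. Treatment, sample size and efficacy analyses are unchanged.
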